8.3 Ethics and regulatory review

An Institutional Review Board (IRB) should approve the final study protocol, including the final version of the informed consent form and any other written information and/or materials to be provided to the healthy volunteers. The investigator will ensure the distribution of these documents to the applicable IRB, and to the study center personnel.

The opinion of the IRB should be given in writing. The investigator should submit the written approval to AstraZeneca before enrolment of any healthy volunteer into the study.

The IRB should approve all advertising used to recruit healthy volunteers for the study.

AstraZeneca should approve any modifications to the informed consent form that are needed to meet local requirements.

If required by local regulations, the protocol should be re-approved by the IRB annually.

Before enrolment of any healthy volunteer into the study, the final study protocol, including the final version of the informed consent form, is approved by the national regulatory authority or a notification to the national regulatory authority is done, according to local regulations.

AstraZeneca will handle the distribution of any of these documents to the national regulatory authorities.

AstraZeneca will provide regulatory authorities, IRB, and principal investigator with safety updates/reports according to local requirements, including suspected unexpected serious adverse reactions (SUSARs), where relevant.

Each principal investigator is responsible for providing the IRB with reports of any serious and unexpected adverse drug reactions from any other study conducted with the investigational product. AstraZeneca will provide this information to the principal investigator so that he/she can meet these reporting requirements.

8.4 Informed consent

The principal investigator will:

- Ensure each healthy volunteer is given full and adequate oral and written information about the nature, purpose, possible risk, and benefit of the study.
- Ensure each healthy volunteer is notified that they are free to discontinue from the study at any time.
- Ensure that each healthy volunteer is given the opportunity to ask questions and allowed time to consider the information provided.
- Ensure each healthy volunteer provides signed and dated informed consent before conducting any procedure specifically for the study. A separate informed consent form will be provided for the optional genotyping.
- Ensure the original, signed informed consent forms are stored in the Investigator's Study File.
- Ensure a copy of the signed informed consent forms are given to the healthy volunteer.
- Ensure that any incentives for healthy volunteers who participate in the study as well as any provisions for healthy volunteers harmed as a consequence of study

participation are described in the informed consent form that is approved by an IRB

8.5 Changes to the protocol and informed consent form

Study procedures will not be changed without the mutual agreement of the principal investigator and AstraZeneca.

If there are any substantial changes to the study protocol, then these changes will be documented in a study protocol amendment and where required in a new version of the study protocol (revised clinical study protocol).

The amendment is to be approved by the relevant IRB and if applicable, also the national regulatory authority approval, before implementation. Local requirements are to be followed for revised protocols.

AstraZeneca will distribute any subsequent amendments and new versions of the protocol to the principal investigator. For distribution to IRB see Section 8.3.

If a protocol amendment requires a change to the study center's informed consent form, AstraZeneca and the study center's IRB are to approve the revised informed consent form before the revised form is used

If local regulations require, any administrative change will be communicated to or approved by the IRB.

8.6 Audits and inspections

Authorized representatives of AstraZeneca, a regulatory authority, or an IRB may perform audits or inspections at the study center, including source data verification. The purpose of an audit or inspection is to systematically and independently examine all study-related activities and documents, to determine whether these activities were conducted, and data were recorded, analyzed, and accurately reported according to the protocol, GCP, guidelines of the ICH, and any applicable regulatory requirements. The investigator will contact AstraZeneca immediately if contacted by a regulatory agency about an inspection at the study center.

9. STUDY MANAGEMENT BY ASTRAZENECA

9.1 Pre-study activities

Before the first healthy volunteer is entered into the study, it is necessary for a representative of AstraZeneca to visit the study center to:

- Determine the adequacy of the facilities.
- Determine availability of appropriate healthy volunteer for the study.

• Discuss with the investigator (and other personnel involved with the study) their responsibilities with regard to protocol adherence, and the responsibilities of AstraZeneca or its representatives. This will be documented in a Clinical Study Agreement between AstraZeneca and the investigator.

9.2 Training of study site personnel

Before the first healthy volunteer is entered into the study, an AstraZeneca representative will review and discuss the requirements of the clinical study protocol and related documents with the investigational staff and also train them in any study specific procedures and system(s) utilized.

The principal investigator will ensure that appropriate training relevant to the study is given to all of these staff, and that any new information relevant to the performance of this study is forwarded to the staff involved.

The principal investigator will maintain a record of all individuals involved in the study (medical, nursing and other staff).

9.3 Monitoring of the study

During the study, an AstraZeneca representative will have regular contacts with the study center, including visits to:

- Provide information and support to the investigator.
- Confirm that facilities remain acceptable.
- Confirm that the investigational team is adhering to the protocol, that data are being accurately and timely recorded in the eCRFs, that biological samples are handled in accordance with the Laboratory Manual and that investigational product accountability checks are being performed.
- Perform source data verification (a comparison of the data in the eCRFs with the healthy volunteer's medical records at the hospital or practice, and other records relevant to the study) including verification of informed consent of participating healthy volunteers. This will require direct access to all original records for each healthy volunteer (eg, clinic charts).
- Ensure withdrawal of informed consent to the use of the healthy volunteer's biological samples is reported and biological samples are identified and disposed of/destroyed accordingly, and the action is documented, and reported to the healthy volunteer.

The AstraZeneca representative will be available between visits if the investigator or other staff at the study center needs information and advice about the study conduct.

9.3.1 Source data

Refer to the Clinical Study Agreement for location of source data.

9.4 Study agreements

The principal investigator at the study center should comply with all the terms, conditions, and obligations of the Clinical Study Agreement, or equivalent, for this study. In the event of any inconsistency between this clinical study protocol and the Clinical Study Agreement, the terms of clinical study protocol shall prevail with respect to the conduct of the study and the treatment of healthy volunteers and in all other respects, not relating to study conduct or treatment of healthy volunteers, the terms of the Clinical Study Agreement shall prevail.

Agreements between AstraZeneca and the principal investigator should be in place before any study related procedures can take place, or healthy volunteers are enrolled.

9.4.1 Archiving of study documents

The investigator will follow the principles outlined in the Clinical Study Agreement.

9.5 Study timetable and end of study

The end of the study is defined as 'the last visit of the last healthy volunteer undergoing the study'.

The study is expected to start in Q4 2013 and to end by Q1 2014.

The study may be terminated at the study center if the study procedures are not being performed according to GCP, or if recruitment is slow. AstraZeneca may also terminate the entire study prematurely if concerns for safety arise within this study or in any other study with selumetinib.

10. DATA MANAGEMENT

Data management will be performed by

A 21 Code of Federal Regulations part 11 compliant electronic data capture (EDC) system, the Phase I Clinical Trial System (PICTS) will be used for this study. Electronic CRFs will be produced for each healthy volunteer. The majority of study data collected will be either

directly entered by clinical research personnel or directly captured from devices onto the eCRF. Data will be available for AstraZeneca review via predefined reports extracted from the database at agreed intervals.

The eCRFs must be kept in order and up-to-date so that they reflect the latest observations on the enrolled healthy volunteers.

When direct data entry into the eCRF is inappropriate or impractical, data will be collected on paper source documents and subsequently transcribed, where necessary, into the eCRFs by the Clinical Research Personnel/ All source documents will be retained by

Photocopies of completed source documents will be provided only if essential (ie, for regulatory purposes) at the request of the AstraZeneca.

Safety laboratory data are managed and stored within the LIMS system and only the date and time of sampling are recorded in the eCRF. Safety laboratory data will be integrated with the consolidated clinical data before database lock.

The informed consent form will be kept with a copy of the completed source documents in the appropriate file folder provided, or a note to indicate where the records can be located. All records should be kept in conformance to applicable national laws and regulations.

Validity and consistency of data will be checked by employing pre-programmed data validation rules that will be applied to the data extracted from the EDC system during the course of the study. The data management team will raise queries in the EDC system to resolve discrepancies. The principal investigator must verify that all data entries in the eCRFs are accurate and correct. After completion of the study and when all collected data is validated, the database will be locked. Final data will be extracted from the EDC and delivered to the AstraZeneca in form of datasets.

All eCRF entries, corrections, and alterations must be made by the principal investigator or other authorized study center personnel and only by individuals who have received training on the EDC system. The study center personnel may be allowed access to the system only after training is completed. Training must be documented and a log of all EDC users and their rights within the system be maintained.

Adverse events and medical history will be coded using the current Medical Dictionary for Regulatory Activities (MedDRA) vocabulary and concomitant medication will be coded using the AstraZeneca Drug Dictionary as appropriate.

The EDC system will keep track of all data entry, alterations, and query resolution in an audit trail. The audit trail will form an integral part of the database and will be archived alongside with the data.

11. EVALUATION AND CALCULATION OF VARIABLES

11.1 Calculation or derivation of safety variable(s)

11.1.1 Calculation of change-from-baseline

Change-from-baseline variables will be calculated for the safety variables listed below, as the posttreatment value minus the value at baseline. The baseline values will be as follows:

- Clinical laboratory tests: last measureable value taken prior to dose in corresponding treatment period.
- Vital signs: last measureable value taken prior to dose in corresponding treatment period.
- Digital ECG: last measureable value taken prior to dose in corresponding treatment period.

If a healthy volunteer is missing the baseline collection, the previous nonmissing evaluation will become the baseline value. If no baseline or previous-to-baseline evaluations exist, then the baseline value will be treated as missing and no change-from-baseline value will be calculated.

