Optional pharmacogenetic sampling		X^{i}				

	Visit 1	Visit 1 Visits 2 and 3 ^a				Visit 4	
Assessments	Screening ≤28 days before Visit 2	Day -1	Day 1	Day 2	Day 3	Follow-up 7 to 10 days after discharge from Visit 3	
Pharmacokinetic blood sampling ^j			X	X	X		
Standard meals ^k			X	X	X		
Concomitant medications recording	X	X	X	X	X	X	
Adverse event recording		X	X	X	X	X	
Serious adverse event recording	X	X	X	X	X	X	

HIV: human immunodeficiency virus

- a Visits 2 and 3 will be separated by a washout period of at least 7 days between doses. Healthy volunteers will be resident at the study center from Day -1 until Day 3 for each visit.
- b Visit 2 only.
- c Ophthalmic examination (best corrected visual acuity, intra-ocular pressure, slit-lamp fundoscopy) will be conducted at screening or Visit 2 Day -1 and will only be repeated on occurrence of an adverse event.
- d Height will only be recorded at screening.
- e A brief physical examination will be performed.
- f Supine pulse rate and blood pressure will be measured at screening, Visits 2 and 3 Day -1, Day 1 at predose, 1.5, 2, 4, 8, and 12 hours postdose, Day 2 (24 hours postdose), Day 3, and at follow-up. Pulse rate and blood pressure will be recorded after the electrocardiogram assessment.
- g Blood samples will be collected at screening, Day -1, Day 2 (24 hours postdose), Day 3 (48 hours postdose), and at follow-up.
- h The 12-lead electrocardiograms will be performed at screening, Day 1 at predose, 1.5, and 8 hours postdose, and at follow-up. Healthy volunteers should be resting in the supine position for 10 minutes before the electrocardiogram recording.
- The pharmacogenetic sample can be collected at any time during the study after optional informed consent has been signed.
- Blood samples (2 mL) will be collected to measure selumetinib and N-desmethyl metabolite at predose, 0.5, 1, 1.5, 2, 2.5, 3, 3.5, 4, 5, 6, 8, 12, 24 (Day 2), 36, and 48 hours (Day 3) postdose. When the pharmacokinetic sampling time points coincide with electrocardiogram and vital signs assessments, the other assessments should be performed before the pharmacokinetic sampling with the pharmacokinetic sampling taking place at the protocol specified time points.

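### The missing-baseline fallback can make a period 1 post-dose ECG or laboratory value the baseline for period 2

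*Protocol*

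**What the plan says.** Section 11.1.1 of the Protocol defines change from baseline "as the posttreatment value minus the value at baseline". It ties baseline to the treatment period. For laboratory data the rule is "Clinical laboratory tests: last measureable value taken prior to dose in corresponding treatment period", for ECG it is "Digital ECG: last measureable value taken prior to dose in corresponding treatment period", and vital signs have the same rule.

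Two sentences on missing baselines follow. The first is the fallback: "If a healthy volunteer is missing the baseline collection, the previous nonmissing evaluation will become the baseline value". The second covers the case where nothing earlier exists: "If no baseline or previous-to-baseline evaluations exist, then the baseline value will be treated as missing", and no change is calculated. Neither sentence restricts the fallback to the same period or to values taken before dosing.

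The schedule is in the footnotes to Table 2 (Section 3.1). For laboratory data: "Blood samples will be collected at screening, Day -1, Day 2 (24 hours postdose), Day 3 (48 hours postdose), and at follow-up". For ECG: "The 12-lead electrocardiograms will be performed at screening, Day 1 at predose, 1.5, and 8 hours postdose, and at follow-up". For vital signs: "Supine pulse rate and blood pressure will be measured at screening, Visits 2 and 3 Day -1, Day 1 at predose", followed by the post-dose readings. The two doses are at least 7 days apart, and no assessment is scheduled between the Visit 2 discharge and the Visit 3 admission.

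**The concern.** In a two-period crossover, a period-specific baseline is meant to remove whatever was present before that period's dose. A fallback that may cross into the earlier period can pick up a value measured after the earlier dose. The period 2 change would then compare two post-treatment values, one fed and one fasted. It would no longer be the quantity that Section 11.1.1 defines.

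The change values are used in two places. Section 11.1.2 tabulates QTcF changes above 30 ms and above 60 ms as outliers. Section 12.2.3 summarises change from baseline for all continuous safety data and allows baseline-to-treatment shift plots. Laboratory variables and ECGs belong to the third secondary objective (Section 2.2). A contaminated baseline could move a volunteer across a threshold in either direction.

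**Working it through.** **Step 1. Confirm the schedule.** Laboratory samples per volunteer from the Table 2 footnotes: 1 screening + 2 periods × 3 (Day -1, 24 h, 48 h) + 1 follow-up = 8. Table 7 (Section 7.1) also gives 8 clinical chemistry and 8 hematology samples, so no further scheduled pre-dose sample has been overlooked. ECGs: 1 screening + 2 × 3 (pre-dose, 1.5 h, 8 h) + 1 follow-up = 8.

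**Step 2. Apply the fallback to the last scheduled value before the missing baseline.**

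| Variable | Period | Scheduled baseline | Previous scheduled value if missing | Taken before any dose? |
|---|---|---|---|---|
| Laboratory | 1 | Visit 2 Day -1 | Screening | Yes |
| Laboratory | 2 | Visit 3 Day -1 | Visit 2 Day 3, 48 h post-dose | No |
| ECG | 1 | Visit 2 Day 1 pre-dose | Screening | Yes |
| ECG | 2 | Visit 3 Day 1 pre-dose | Visit 2 Day 1, 8 h post-dose | No |
| Vital signs | 1 | Visit 2 Day 1 pre-dose | Visit 2 Day -1 | Yes |
| Vital signs | 2 | Visit 3 Day 1 pre-dose | Visit 3 Day -1 | No, but pre-dose in the same period |

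Only period 2 is affected and, for a single missing value, only laboratory and ECG data. Vital signs reach Visit 2 Day 3 only if both Visit 3 pre-dose readings are missing.

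**Step 3. Effect on the change.** Let B be the volunteer's drug-free level, d(t) the deviation from B at time t in period 2, and e the deviation from B in the period 1 value used as substitute.

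- Intended change: (B + d(t)) − B = d(t).
- Change under the fallback: (B + d(t)) − (B + e) = d(t) − e.
- Error: −e.

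For the 30 ms QTcF flag, the condition d(t) > 30 becomes d(t) > 30 + e. If e is positive, values with 30 < d(t) ≤ 30 + e lose the flag. If e is negative, values with 30 + e < d(t) ≤ 30 gain one. The 60 ms flag behaves in the same way. The documents give no value for e, so no size can be attached to it.

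**Step 4. How many volunteers.** The documents give no missing rate. Assuming 2-3% for one variable: 34 × 0.02 = 0.68 and 34 × 0.03 = 1.02, so about one volunteer per variable.

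**Step 5. How much older a drug-free substitute would be.** At the minimum washout the Visit 3 dose falls 7 × 24 = 168 h after the Visit 2 dose. The 8 h ECG is then 168 − 8 = 160 h before the Visit 3 dose. The Visit 2 pre-dose ECG is at most one hour before the Visit 2 dose (Section 6), so 168 to 169 h before: only 8 to 9 h older. For laboratory data, Visit 2 Day -1 is about three days older than the Day 3 sample, which lies 168 − 48 = 120 h before the Visit 3 dose.

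**The case against.** The strongest counter-argument is that the fallback should be read within the period. The three definitions directly above it are all period-specific. If the search may cross periods, screening values exist for nearly everyone, so the sentence leaving baseline missing would almost never apply. The text is therefore open to more than one reading. But the definitions already take the last measurable pre-dose value in the period, so a fallback confined to those values has nothing left to find. It can act only by leaving the period, and nothing written then excludes post-dose values.

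Several further points stand and limit the impact:

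- Volunteers are resident from Day -1, and Sections 6.3.5 and 6.3.7 allow repeat laboratory tests and additional ECGs. A lost sample or failed recording may be redone before dosing, and that value would be the in-period baseline. An unscheduled washout value would also displace the Visit 2 value.
- The absolute QTcF limits (450, 480 and 500 ms) do not use baseline. Abnormal or out-of-range laboratory values are flagged in the listings whatever the baseline, and all safety data are listed.
- Shift plots are produced only where judged appropriate.

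A reader might infer that both substitutes are on-drug values. That is reasonable for an ECG 8 h after dosing. For the 48 h laboratory sample, only its being post-dose is certain: the Protocol states no half-life, so residual drug cannot be shown. A reader might also infer that a real drug effect would be cancelled. The documents do not establish one. Section 1.3.1 reports no clinically important laboratory or ECG trends in healthy volunteers given single 75 mg capsule doses on three occasions.

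Finally, leaving the change missing would sit at least as well with Section 12.2.3, which rules out imputing missing safety values, as an older substitute would. Both are acceptable provided the choice is written down.

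**Conclusion.** The point holds as a minor defect in a stated rule. As written, the fallback permits a period 1 post-dose value to serve as the period 2 baseline for ECG and laboratory data, against the period-specific definition in the same section. The resulting change is post-treatment minus post-treatment across food conditions, and it can err in either direction.

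The effect is confined to a volunteer who has no Visit 3 pre-dose value, scheduled or unscheduled, and no washout value: at most about one of 34 per variable on the assumed 2-3% missing rate. It concerns descriptive safety outputs only. The pharmacokinetic endpoints, the food-effect ratios and that volunteer's period 1 changes are untouched. The documents do not support a claim that a safety signal would be lost; they support only that the rule could shift a change flag or a laboratory shift for that volunteer.

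**What to change.** Replace the fallback sentence in Section 11.1.1 with wording to this effect: post-dose values from the earlier treatment period are never used as baseline; if a period has no pre-dose value, the last value before the first dose of selumetinib is used and identified as a substitute in the listing; if there is none, change from baseline is missing.

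For period 2 this moves the ECG substitute from Visit 2 at 8 h to the Visit 2 pre-dose recording, and the laboratory substitute from Visit 2 Day 3 to Visit 2 Day -1, or to screening if those too are missing. The period 1 fallback is unchanged.

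The cost is one sentence and one programming condition. The downside is an older baseline, or a missing change, for the volunteer concerned. The extra age is small when a Visit 2 pre-dose value exists and larger when only screening is available, since screening may be up to 28 days before Visit 2.

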11.1.2 Other significant adverse events

During the evaluation of the AE data, an AstraZeneca medically qualified expert will review the list of AEs that were not reported as SAEs and discontinuations of the investigational product due to an AE (DAEs). Based on the expert's judgment, significant AEs of particular clinical importance may, after consultation with the AstraZeneca Clinical Pharmacology Alliance Physician, be considered as other significant AEs (OAEs) and reported as such in the clinical study report. A similar review of laboratory/vital signs data will be performed for identification of OAEs.

Examples of these are marked hematological and other laboratory abnormalities, and certain events that lead to intervention (other than those already classified as serious), dose reduction or significant additional treatment.

Any asymtomatic deviation in ECG/telemetry intervals, amplitudes, or morphology that is deemed not to constitute a safety concern for the individual healthy volunteer, nor to require a change in healthy volunteer care, surveillance, or study participation is to be reported qualitatively as an outlier value or with a narrative in the clinical study report. This includes also eg, short, asymptomatic, accidentally found paroxysmal supraventricular tachycardia or nonsustained ventricular tachycardia with characteristics that are normally not associated with investigational product exposure:

Extra measurements (such as unscheduled or repeat assessments) will not be included in the descriptive statistics, but will be included in data listings. All AEs, ECG outliers for QTcF

 V_z/F

(ie, greater than 450, greater than 480, greater than 500 ms, or change-from-baseline greater than 30 and greater than 60 ms) and clinical laboratory outliers that occur following the first dose of investigational product will be included in the tabulations of AEs and outlier events, including episodes that occur at unscheduled evaluations or during the washout period between treatments.

